# Management of anemia

Table 7 Management of anemia

Hemoglobin	Action to be taken	
Hb < 10 but ≥ 8 g/dl (CTCAE Grade 2)	Give appropriate supportive treatment and investigate causality. Investigator judgement to continue olaparib with supportive treatment (eg transfusion) $or$ interrupt dose for a maximum of 2 weeks. If repeat Hb < 10 $but \ge 8$ g/dl, dose interrupt (for max of 2 weeks) until Hb $\ge 10$ g/dl and upon recovery dose reduction to 250 mg twice daily as a first step and to 200 mg twice daily as a second step may be considered.	
Hb < 8 g/dl (CTCAE Grade 3)	Give appropriate supportive treatment (e.g. transfusion) and investigate causality.  Interrupt olaparib for a maximum of 2 weeks until improved to Hb ≥ 10 g/dl.  Upon recovery dose reduce to dose should be reduced to 200 mg twice daily as first step. If the reduced dose of 200 mg twice daily is not tolerable, no further dose reduction is allowed and study treatment must be discontinued.	

Common treatable causes of anemia (e.g. iron, vitamin B12, or folate deficiencies and hypothyroidism) should be investigated and appropriately managed. In some cases management of anemia may require blood transfusions.

Management of neutropenia, leukopenia and thrombocytopenia

Table 8 Management of neutropenia, leukopenia and thrombocytopenia

Toxicity	Study treatment dose adjustment
CTCAE Grade 1-2	Investigator judgement to continue treatment or if dose interruption, this should be for a maximum of 2 weeks; appropriate supportive treatment and causality investigation
CTCAE Grade 3-4	Dose interruption until recovered to CTCAE grade 1 or better for a maximum of 2 weeks. If repeat CTCAE grade 3-4 occurrence, dose reduce olaparib to 250 mg twice daily as a first step and 200 mg twice daily as a second step
	Discontinue therapy in cases of febrile neutropenia and thrombocytopenia associated with hemorrhage

Adverse event of neutropenia and leukopenia should be managed as deemed appropriate by the investigator with close follow up and interruption of study drug if CTCAE grade 3 or worse neutropenia occurs.

Primary prophylaxis with granulocyte colony-stimulating factor (G-CSF) is not recommended, however, if a patient develops febrile neutropenia, study treatment should be stopped and appropriate management including G-CSF should be given according to local hospital guidelines. Please note that G-CSF should not be used within at least 24 h (7 days for PEGylated G-CSF) of the last dose of study treatment unless absolutely necessary.

Platelet transfusions, if indicated, should be done according to local hospital guidelines.

## Management of prolonged hematological toxicities while on study treatment

Discontinue olaparib if a patient develops prolonged hematological toxicity such as:

≥2 week interruption/delay in study treatment due to CTCAE grade 3 or worse anemia and/or development of blood transfusion dependence

 $\geq$ 2 week interruption/delay in study treatment due to CTCAE grade 3 or worse neutropenia (ANC <1 x 10 $^{9}$ /L)

 $\geq$ 2 week interruption/delay in study treatment due to CTCAE grade 3 or worse thrombocytopenia and/or development of platelet transfusion dependence (Platelets <50 x 10 $^{\circ}$ /L)

Adverse events possibly must be resolved to grade 1 or baseline prior to resumption of dosing. Study treatment should be discontinued if blood counts do not recover to CTCAE grade 1 or better within 4 weeks of dose interruption.

Check weekly differential blood counts including reticulocytes and peripheral blood smear. If any blood parameters remain clinically abnormal after 2 weeks of dose

interruption, the patient should be referred to hematologist for further investigations. Bone marrow analysis and/or blood cytogenetic analysis should be considered at this stage according to standard hematological practice. Development of a confirmed myelodysplastic syndrome or other clonal blood disorder should be reported as an SAE and full reports must be provided by the investigator to AstraZeneca Patient Safety. Olaparib treatment should be discontinued if patient's diagnosis of MDS and/or AML is confirmed.

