# 7.4 Duration of Therapy and Criteria for Removal from Study

Patients will be removed from study when any of the criteria listed apply. The reason for study removal and the date the patient was removed must be documented in the Case Report Form.

In the absence of treatment delays due to adverse event(s), treatment may continue until one of the following criteria applies:

- Disease progression by RECIST criteria v1.1 (Appendix E) or bone progression per PCWG3 (see Section 7.4.1)
- Disease progression by symptomatic assessment
- PSA doubling from baseline value, confirmed by a second value at least 4 weeks apart, with a minimum time since initiation of therapy of 12 weeks (see **Section 7.4.1**)
- Intercurrent illness that prevents further administration of treatment
- Unacceptable adverse event(s): toxicity (defined in **Section 8.1**) that has not recovered in 2 weeks or if the same toxicity recurs at the decreased dose (unless there is strong evidence of clinical benefit to justify continuation of dosing with study treatment, and the rationale must be discussed with the Principal Investigator before a decision is made)
- The subject or legal representative (such as a parent or legal guardian) withdraws consent for treatment
- If, in the opinion of the Investigator, a change or temporal or permanent discontinuation of therapy would be in the best interest of the subject
- Patient is noncompliant with respect to taking drugs, keeping appointments, or having tests required
- for the evaluation of drug safety and efficacy Bone marrow findings consistent with myelodysplastic syndrome (MDS)/acute myeloid leukemia (AML)
- Potential Hy's Law cases (AST or ALT ≥3x ULN and TBL ≥2x ULN with no other reason)

Because an excessive rate of withdrawals can render the study uninterpretable, unnecessary withdrawal of patients should be avoided. When a patient discontinues

treatment early, the investigator should make every effort to contact the patient and to perform a final evaluation. The reasons for withdrawal should be recorded.

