# 8.0 DOSING DELAYS/MODIFICATIONS

# 8.1 Dosing Delays

All scheduled cycles occur over a 28-day period. If necessary, treatment may be delayed for up to 4 weeks. If treatment is delayed more than two weeks, the Principal Investigator must be contacted for further instructions on continued treatment. Additional delays or modifications to the treatment schedule must be approved by the Protocol Chair. When the delay is due to toxicity, then the next cycle may begin with a dose reduction.

Ascorbic acid will be withheld for the following drug-related toxicities:

- $Cr \ge 1.6 \times ULN$  (for patients with  $Cr \ge 1.6 \times ULN$ , calculated or measured creatinine clearance must be  $\ge 50 \text{ mL/minute}$  (Cockcroft-Gault))
- Common Terminology Criteria for Adverse Events (CTCAE) Grade 3 or 4 non-hematologic toxicity excluding asymptomatic electrolyte aberrations
- Any AE, laboratory abnormality, or intercurrent illness that, in the judgement of the investigator, warrants delaying the dose of study medication

Olaparib will be withheld for the following drug-related toxicities:

Absolute neutrophil count
 Platelets
 Hemoglobin
 Total bilirubin
 AST (SGOT)/ALT(SGPT)
 ≤ 750/ mm³, see Table 8
 ≤ 8 hgb, If < 10, see Table 7

 ≥ 1.5XULN
 ≥ 2.5 x ULN (<5x ULN if with known liver m

• AST (SGOT)/ALT(SGPT)  $\geq 2.5 \text{ x ULN (<}5\text{x ULN if with known liver metastases}$  provided bilirubin is normal)

- Common Terminology Criteria for Adverse Events (CTCAE) Grade 3 or 4 non-hematologic toxicity excluding asymptomatic electrolyte aberrations
- Any AE, laboratory abnormality, or intercurrent illness that, in the judgement of the investigator, warrants delaying the dose of study medication

If dosing parameters for Ascorbic Acid are not met, study participants may continue with olaparib therapy. If dosing parameters for olaparib or are not met, study participants may continue with Ascorbic Acid therapy. Dose interruptions are allowed as required, for a maximum of 4 weeks. Patients who require an interruption in olaparib or ascorbic acid for >4 weeks due to toxicity must permanently discontinue study drug unless an exemption is granted by the protocol chair (Refer to section 13.6 for stopping rule). Where toxicity reoccurs following re-challenge with study treatment, then the patient should be considered for dose reduction or must permanently discontinue study treatment per investigator judgement.

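### For grade 3 or worse blood toxicity, some sections point to stopping olaparib at 2 weeks and others allow interruption up to 4 weeks, with no stated precedence

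*Combined protocol and SAP*

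**What the plan says.** Text pointing to 2 weeks:

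- Section 8.2.2.3, prolonged hematological toxicities: olaparib is discontinued for events such as "≥2 week interruption/delay in study treatment due to CTCAE grade 3 or worse anemia and/or development of blood transfusion dependence". Neutropenia and thrombocytopenia have parallel entries.
- Table 7, grade 3 anemia: "Interrupt olaparib for a maximum of 2 weeks until improved to Hb ≥ 10 g/dl", then a reduced dose on recovery.
- Table 8, grade 3-4 neutropenia, leukopenia or thrombocytopenia: "Dose interruption until recovered to CTCAE grade 1 or better for a maximum of 2 weeks".
- Section 7.4 ends treatment for a toxicity "that has not recovered in 2 weeks or if the same toxicity recurs at the decreased dose", but adds an exception: "unless there is strong evidence of clinical benefit to justify continuation of dosing with study treatment".

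Text pointing to 4 weeks:

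- The same prolonged-toxicity subsection, after its list: "Adverse events possibly must be resolved to grade 1 or baseline prior to resumption of dosing", followed by "Study treatment should be discontinued if blood counts do not recover to CTCAE grade 1 or better within 4 weeks of dose interruption".
- Section 8.1 opens a list that includes blood counts with "Olaparib will be withheld for the following drug-related toxicities" and refers to Tables 7 and 8. It then permits interruptions of up to 4 weeks without excepting blood counts. Delays beyond two weeks require contact with the Principal Investigator.
- The opening of Section 8.2.2.3 ends all study therapy when an olaparib interruption for toxicity exceeds 4 weeks.

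Section 8.2 adds a further rule: a grade 3 or 4 toxicity that has come down to grade 0-2 after a two-week delay is re-treated at a reduced dose.

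**The concern.** A patient whose grade 3 cytopenia recovers in the third or fourth week meets the condition for stopping olaparib in the 2-week list. The same patient also meets the recovery condition for dosing again and is inside every 4-week limit. The protocol does not say which text prevails.

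The 2-week point is also where this subsection calls for hematology referral and consideration of marrow or cytogenetic analysis. Whether to re-expose such a patient to a PARP inhibitor is a safety decision. In a multi-center study of 12 to 15 patients, the answer should not depend on which sentence is read.

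**Working it through.** **Text comparison.** Take a grade 3 neutropenia with olaparib held from day 0, and read each rule against the day of recovery.

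| Course | 2-week list (8.2.2.3) | Table 8 | Section 7.4 | Section 8.2 | 4-week sentences (8.2.2.3, 8.1) |
|---|---|---|---|---|---|
| Grade 1 on day 10 | Not triggered | Within cap | Not triggered | Not yet at two weeks | Not triggered |
| Grade 1 on day 14 | Stop (2 weeks reached) | Full 2 weeks allowed, recovered | Recovered in time | Reduce dose and continue | Not triggered |
| Grade 2 on day 14 | Stop | Cap reached, consequence not stated | Depends on what counts as recovered | Reduce dose and continue | Not triggered; resumption needs grade 1 or baseline |
| Grade 1 on day 20 | Stop | Cap exceeded, consequence not stated | Stop, unless clinical benefit | Silent on delays over two weeks | Not triggered; resumption condition met |
| Not recovered after day 28 | Stop | Cap exceeded | Stop, unless clinical benefit | Not met | Stop, unless the Protocol Chair exempts under 8.1 |

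The first row is consistent. The last agrees on stopping, apart from the stated exemptions. The middle three are not settled.

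**Is it a strict contradiction?** For day 20, no. Call the list rule A (interruption of 2 weeks or more: stop), the 4-week sentence rule B (no recovery by 4 weeks: stop), and the resumption sentence rule C (dosing may restart only after resolution). Stopping at 2 weeks satisfies A. It leaves B with nothing to act on and never invokes C. Section 8.1 and the opening of Section 8.2.2.3 set outer limits, and a shorter limit fits inside them.

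Under that reading, however, B does nothing for olaparib in the three listed cytopenias, because every such patient has already stopped. B also directly follows a sentence about resuming dosing. A reader who assumes that B has a purpose will take it as permission to wait 4 weeks.

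For day 14 the conflict is direct. The list says stop, while Section 8.2 says reduce the dose and continue, and Table 8 still permits the interruption. Table 7 does the same for anemia and expressly restarts at 200 mg twice daily on recovery. The recovery grade differs as well: 0-2 in one sentence of Section 8.2, but grade 1 or baseline elsewhere in Section 8.2 and in Section 8.2.2.3.

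**How often will the rule be consulted?** The documents report grade 3-4 anemia on olaparib alone at 17.4% (Table 1, 298 patients) and 20% (Section 4.2.6, 50 patients at 400 mg twice daily).

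- Expected in 12 patients: 12 × 0.174 = 2.09; 12 × 0.20 = 2.40.
- Chance of at least one in 12: 1 − 0.826^12 = 0.899; 1 − 0.80^12 = 0.931.
- Expected in 15 patients: 15 × 0.174 = 2.61; 15 × 0.20 = 3.00. Chance of at least one: 0.943; 0.965.
- Exact 95% intervals: 52/298 gives 13.3% to 22.2% (1.6 to 2.7 of 12); 10/50 gives 10.0% to 33.7% (1.2 to 4.0 of 12). The count 52 is 0.174 × 298 = 51.9, rounded.

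These figures count any grade 3-4 anemia. The share f that recovers in weeks 2 to 4 is not given. If f were assumed to be 10%, the expected number in 12 would be 0.10 × 2.09 = 0.21 to 0.10 × 2.40 = 0.24. Across f from 0 to 1 it runs from 0 to 2.09 or 2.40 at those rates. This is an illustration for anemia only, not a bound.

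**Link to safety monitoring.** Section 13.6 counts grade 3-4 events that have not resolved to grade 2 after four weeks off drug. Tables 9 and 10 use that definition and do not depend on whether olaparib stops at 2 or 4 weeks, provided that counts are observed to 4 weeks.

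**The case against.** The strongest defense is that the protocol can be followed without breaking any sentence: apply the 2-week rule. It is the stricter and more specific rule. Section 8.1 sends blood-count holds to Tables 7 and 8, which carry the 2-week cap. The 4-week sentences say when treatment must stop, not that it may continue. This stands. A reader might infer that any decision in weeks 2 to 4 violates some part of the protocol, or that resumption is expressly granted. Neither follows, since the resumption sentence is a necessary condition and not a permission. What remains is that nothing tells the reader to prefer the stricter rule, and that the defense does not reach the day-14 clash.

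A second defense is a two-tier rule: olaparib stops at 2 weeks, everything including ascorbate at 4. The list names olaparib while the 4-week sentence names study treatment, Section 12.4 uses that term for both agents, and Section 8.1 lets ascorbate continue alone. The reading is available but unstated. Table 4 uses study treatment for olaparib doses only, and the opening of Section 8.2.2.3 adds the word all when it means both agents.

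A third is that the 4-week sentence covers what the list omits: leukopenia and lower grades. Tables 7 and 8 cap interruptions at 2 weeks for leukopenia, grade 2 anemia and grade 1-2 counts as well, without saying what follows, so the sentence may supply that consequence. But it is not limited to those cases.

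Finally, beyond two weeks the Principal Investigator must be consulted. That reduces divergence between sites, but it supplies no limit to apply, and a delay of exactly two weeks does not trigger it.

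**Conclusion.** The concern holds as an inconsistency without stated precedence. For grade 3 or worse hematological toxicity, the text leans to stopping olaparib at 2 weeks but also supports resuming after recovery in weeks 2 to 4. At day 14 its instructions conflict outright. The recovery grade for retreatment is also inconsistent.

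The size in patients cannot be computed, because the share recovering in weeks 2 to 4 is not in the documents. A reader might take the 2.1 to 2.4 of 12 as the number affected, or as its ceiling. It is neither: it is a point estimate for any grade 3-4 anemia on monotherapy, and carrying it over assumes that the combination has a similar rate. It shows only that the rule is likely to be needed.

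A reader might also suspect an effect on the PSA50 result or on the safety boundaries. The documents give no basis for that, and none is claimed. The text should be corrected because it is a safety instruction that can be read two ways.

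**What to change.** State one limit for grade 3 or worse hematological toxicity and align the other sections:

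1. In the prolonged-toxicity subsection of Section 8.2.2.3, replace the three triggers of 2 weeks or more with: discontinue olaparib permanently if grade 3 or worse hematological toxicity has not recovered to grade 1 or better (Hb ≥10 g/dl for anemia) by the end of a 2-week interruption. Recovery on day 14 is then no longer a stop.
2. Delete the 4-week sentence there, or restrict it explicitly to stopping all study treatment including ascorbate. State whether ascorbate may continue once olaparib has stopped.
3. In Section 8.1 and the opening of Section 8.2.2.3, except grade 3 or worse hematological toxicity from the 4-week olaparib limit. Leave the non-hematological rules alone.
4. In Section 8.2, align the grade 0-2 retreatment threshold with grade 1 for blood counts. In Section 7.4, say whether the clinical-benefit exception applies to blood toxicity.
5. Keep following counts to 4 weeks after olaparib stops, so that the Section 13.6 event can still be scored. The weekly counts already required for prolonged toxicity serve this purpose.

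The cost is protocol wording, plus one clinical downside: some patients who would have recovered in weeks 2 to 4 lose olaparib. If the sponsor prefers 4 weeks, the 2-week list, Tables 7 and 8, and Section 7.4 would have to change instead. Tables 9 and 10 and the prior need no change.

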### Bone marrow or blood cytogenetic analysis

Bone marrow or blood cytogenetic analysis may be performed according to standard hematological practice for patients with prolonged hematological toxicities. Bone marrow analysis should include an aspirate for cellular morphology, cytogenetic analysis and flow cytometry, and a core biopsy for bone marrow cellularity. If it is not possible to conduct cytogenetic analysis or flow cytometry on the bone marrow aspirate, then attempts should be made to carry out the tests on a blood sample. If findings are consistent with MDS/AML, study drug should be discontinued and a full description of findings should be submitted with an SAE report by the investigator to AstraZeneca Patient Safety for documentation on the Patient Safety database. Presence or absence of blood cytogenetic abnormalities and flow cytometry will be documented on the clinical database.

# Management of non-hematological toxicity

Dose interruptions are allowed as required, for a maximum of 4 weeks. Patients who require an interruption in study drug >4 weeks due to toxicity must discontinue study drug. Where toxicity reoccurs following re-challenge with study treatment, then the patient should be considered for dose reduction or must permanently discontinue study treatment.

Olaparib can be dose reduced to 250mg bid as a first step and to 200mg bid as a second step. Treatment must be interrupted if any NCI-CTCAE grade 3 or 4 adverse event occurs which the investigator considers to be related to administration of study treatment.

Adverse events possibly related to study drug must be resolved to grade 1 or baseline prior to resumption of dosing.

**Note**: In case a patient shows an AST or ALT  $\geq 3$  ULN or total bilirubin  $\geq 2$  ULN please refer to **Appendix D** 'Actions required in cases of combined increase of Aminotransferase and Total Bilirubin – Hy's Law', for further instructions. Potential Hy's Law cases (AST or ALT  $\geq 3x$  ULN and TBL  $\geq 2x$ ULN with no other reason) must discontinue the study.

# Management of new or worsening pulmonary symptoms

If new or worsening pulmonary symptoms (e.g., dyspnea) or radiological abnormalities occur in the absence of a clear diagnosis, an interruption in study treatment dosing is recommended and further diagnostic workup (including a high resolution CT scan) should be performed to exclude pneumonitis.

Following investigation, if no evidence of abnormality is observed on CT imaging and symptoms resolve, then study treatment can be restarted, if deemed appropriate by the investigator. If significant pulmonary abnormalities are identified, these need to be discussed with the Principle Investigator.

## Management of nausea and vomiting

Events of nausea and vomiting are known to be associated with olaparib treatment. In study D0810C00019 nausea was reported in 71% of the olaparib treated patients and 36% in the placebo treated patients and vomiting was reported in 34% of the olaparib treated patients and 14% in the placebo treated patients. These events are generally mild to moderate (CTCAE grade 1 or 2) severity, intermittent and manageable on continued treatment. The first onset generally occurs in the first month of treatment for nausea and within the first 6 months of treatment for vomiting. For nausea, the incidence generally plateaus at around 9 months, and for vomiting at around 6 to 7 months.

No routine prophylactic anti-emetic treatment is required at the start of study treatment, however, patients should receive appropriate anti-emetic treatment at the first onset of nausea or vomiting and as required thereafter, in accordance with local treatment practice guidelines. Alternatively, olaparib tablets can be taken with a light meal/snack (i.e. 2 pieces of toast or a couple of biscuits).

As per international guidance on anti-emetic use in cancer patients (ESMO, NCCN), generally a single agent antiemetic should be considered e.g. dopamine receptor antagonist, antihistamines or dexamethasone.

## Interruptions for intercurrent non-toxicity related events

Study treatment dose interruption for conditions other than toxicity resolution should be kept as short as possible. If a patient cannot restart study treatment within 4 weeks for resolution of intercurrent conditions not related to disease progression or toxicity, the case should be discussed with Principle Investigator.

All dose reductions and interruptions (including any missed doses), and the reasons for the reductions/interruptions are to be recorded in the eCRF.

Study treatment should be stopped at least 3 days prior to a planned surgery. After surgery study treatment can be restarted when the wound has healed. No stoppage of study treatment is required for any needle biopsy procedure.

Study treatment should be discontinued for a minimum of 3 days before a patient undergoes radiation treatment. Study treatment should be restarted within 4 weeks as long as any bone marrow toxicity has recovered.

Because the AEs related to olaparib may include asthenia, fatigue and dizziness, patients should be advised to use caution while driving or using machinery if these symptoms occur.

